9.3 Arm 2: MK-3475 (Pembrolizumab)

REQUIRED STUDIES		Pre-study Screen		Randomization		ON TREATMENT ^a						End of treatment assessment ^b		Post-treatment F/U prior to relapse ^c		Re-lapse/Recurrence		F/U post relapse ^d	
PHYSICAL	Reg Step 1	Reg Step 2	Reg Step 2	Cycle 1	Cycle 2	C3	C4	C5	C6										
History & Physical (w/ BSA, BP, Height & Weight) ^t	X		X		X	X	X	X	X	*W 13	*W 19	*W 25	*W 31	*W 37	*W 43	*W 49			
PS & Toxicity Notation	X		X		X	X	X	X	X								X	X	
FORMS FOR QOL STUDIES																			
Cover Sheet for Patient-Completed Questionnaires			X	X		X		X	X							X ^r	X ^s		
FACT-BRM, EQ-5D-3L, and FACIT-D Questionnaire			X	X		X		X	X							X ^r	X ^s		
LABORATORY^e																			
ANC, platelets, Hgb	X		X		X	X	X	X	X							X	X	X	
Total bilirubin	X		X		X	X	X	X	X							X	X	X	
LDH ^f	X																	X ^f	
AST and ALT, Alkaline Phosphatase	X		X		X	X	X	X	X							X	X	X	
Serum Creatinine or CrCl	X		X		X	X	X	X	X							X	X	X	
Albumin, Glucose, Na, K, HCO ₃ (or CO ₂) ^a			X ^a		X	X	X	X	X							X	X	X	
Triglycerides ^g	X															X ^g			
Free T ₃ , TSH, Free T ₄ ^o	X							X ^o								X ^o	X ^o	X	
Pregnancy Test ⁱ	X					X ⁱ	X ⁱ	X ⁱ	X ⁱ							X ⁱ	X ⁱ	X	
Cardiac Function ^j			X		X	X	X	X	X							X	X	X	

Study Calendar 9.3 continued on next page. Click here for [footnotes](#).

9.3 Arm 2: MK-3475 (Pembrolizumab) (contd.)

		ON TREATMENT ^a						End of treatment assessment ^b		Post treatment F/U prior to relapse ^c	Re-lapse/R-ecurrence	F/U post relapsed ^d
		The first two cycles consist of 2 infusions, subsequent cycles consist of 4 infusions. Infusions to be given q 3 weeks for 18 total infusions (5.5 cycles).										
	Pre-study Screen	Randomization	Cycle 1	Cycle 2	C3	C4	C5	C6				
	Reg Step 1	Reg Step 2	*W ₁	*W ₄	*W ₇	*W ₁₀	*W ₁₃	*W ₁₉	*W ₂₅	*W ₃₁	*W ₃₇	*W ₄₃
X-RAYS AND SCANS												
Whole body PET/CT or CT neck, chest, abdomen & pelvis	X				X		X		X		X ^{j,k}	
Brain MRI or CT with contrast	X									X ^k		
EKG ^h	X											
Image Submission	X				X		X		X		X	
SPECIMEN SUBMISSION												
Slides for PD-L1 expression ^l	X			X	X	X	X		X			
Serum for PK/ADA ^q										X ^q		
E-mail confirmation tissue was adequate for PD-L1 analysis		X										
Tissue ^m for banking		X									X	
Serum ^m for banking		X ⁿ				X		X			X	
Plasma & Buffy Coat ^m for RNA/DNA for banking		X ⁿ			X		X				X	
TREATMENT												
MK-3475 (Pembrolizumab)			X	X	X	X	X	X	X	X	X	

Study Calendar 9.3 continued. Click here for [footnotes](#).

NOTE: Forms are found on the protocol abstract page of the SWOG website (www.swog.org). Form submission guidelines are found in [Section 14.0](#).

NOTE: Unless indicated otherwise in the protocol, scheduled procedures and assessments (treatment administration, toxicity assessment for continuous treatment, disease assessment, specimen collection and follow-up activities) must follow the established SWOG guidelines as outlined in <https://www.swog.org/sites/default/files/docs/2017-10/Best%20Practices%20Update.pdf>.

Footnotes for Study Calendar 9.3: Arm 2 MK-3475 (Pembrolizumab)

- a. Following exams & labs are performed prior to receiving first dose & prior to every other infusion until end of protocol treatment: physical (w BSA, BP & WT), PS, toxicity notation, ANC, platelets, Hgb, total bilirubin, AST and ALT, alk phos, serum creatinine or CrCl, albumin, glucose, Na, K, HCO₃ (or CO₂). Adverse Event Assessments on the study will continue for all patients until 30 days after the last study drug administration. However, patients with ongoing toxicities should be seen more often as clinically indicated.
- b. End of treatment assessment occurs at the 18th infusion or whenever patient comes off treatment.
- c. Post-treatment follow-up (prior to relapse): Patients should be seen at 6 weeks (-/+ 1 week) after the last dose, then 12 weeks (-/+ 1 week) after the last dose, then every 3 months (-/+ 2 weeks) if patient is < 2 years from study entry, every 6 months (-/+ 4 weeks) if patient is 2-5 years from study entry, and every 12 months (-/+ 4 weeks) if patient is > 5 years from study entry for up to 10 years. The first two follow-up visits may be scheduled to allow follow-up visits and scans to occur on the same date for on-going follow-up. The following exams and labs should be performed: physical (w BSA, BP & wt), PS, ANC, platelets, Hgb, total bilirubin, AST and ALT, alk phos, serum creatinine or CrCl, albumin, glucose, Na, K, HCO₃ (or CO₂). Adverse Event Assessments on the study will continue for all patients until 30 days after the last study drug administration. However, patients with ongoing toxicities should be seen more often as clinically indicated. For post-treatment follow-up regarding scans, see footnote [K](#).
- d. Follow-up post relapse: Patients who develop recurrent melanoma will be followed for survival (vital status). Adverse Events Assessment on the study will continue for all patients until 30 days after the last study drug administration. Patients should be followed every 6 months for up to 2 years from the date of treatment discontinuation, then annually thereafter until 10 years from date of randomization. However, patients with ongoing toxicities should be seen more often as clinically indicated.
- e. While on study, blood samples collected for pretreatment laboratory tests may be collected and analyzed no more than 3 days prior to dosing. NOTE: if MK-3475 was delayed per the dose delay/scheduling criteria or if a visit had to be delayed due to major circumstances (such as a health emergency, family/personal emergency, transportation difficulties, scheduling difficulties; a visit date falls on a holiday), the study assessments scheduled for these dates will be delayed.
- f. LDH to be done at baseline and at relapse.
- g. Triglycerides to be done at screening, after 6 months of treatment and at the end of treatment.
- h. To be performed prior to Registration Step 1, then as clinically indicated. Also see footnote "V".
- i. Women of child bearing potential must have a negative serum or urine pregnancy test at screening within 28 days prior to registration. Following randomization, serum or urine pregnancy tests are required within 72 hours prior to the first dose of study treatment, then according to institutional practice during therapy, tests should coincide with clinic visits for blood work and ending with the discontinuation of study treatment. At discontinuation, a negative pregnancy test within the preceding 6 weeks is sufficient. A pregnancy test should be done at any time there are clinical concerns for possible pregnancy.
- j. Patients with primary melanoma of the head and neck or unknown primary with disease in the axilla will also require a neck CT.
- k. Disease assessments by PET-CT or CT chest/abdomen/pelvis (or MRI if CT cannot be done), and neck CT as needed will be performed every 12 weeks (-/+ 2 weeks) until 2 years from randomization, then every 6 months (-/+ 4 weeks) until 5 years from randomization, then follow for survival. The same imaging modality as used at prestudy for disease assessment should be used throughout the trial. During treatment and follow-up, brain MRI/CT or other imaging studies must be repeated annually (-/+ 4 weeks). For PET-CT imaging, iodinated contrast is recommended in addition to FDG for optimal relapse detection. If there is a contra-indication to iodine, non-contrast chest CT and MRI of abdomen/pelvis with gadolinium are acceptable body imaging alternatives. If there is a gadolinium allergy, or MRI brain intolerable for the patient, CT with iodinated IV contrast is adequate brain imaging. MRI of the brain is required for patients with progressive disease.
- l. Slides must be submitted as described in [Section 15.2](#). Patients cannot be randomized to Step 2 until e-mail notification has been received indicating that the specimen was adequate for determining PD-L1 status.
- m. If patient consents, submit specimens for banking as specified in [Section 15.0](#).
Footnotes for Study Calendar 9.3: Arm 2 MK-3475 (Pembrolizumab) (contd. on next page)

- n. Blood needs to be drawn prior to treatment.
- o. Thyroid function tests to be done at screening, within 3 days prior to the start of study treatment on Week 13, Week 25 and Week 37 and at initial post treatment follow-up. Additional testing to be done as clinically indicated.
- p. Submit scans as outlined in Sections 14.0 and 15.0.
- q. Serum for PK and anti-MK-3475 antibody testing must be submitted for all patients randomized to the MK-3475 arm as described in Section 15.4. Pre-dose trough PK and anti-MK-3475 samples will be collected before the first infusion Cycle 1 (Week 1), before second infusion Cycle 1 (Week 4), before second infusion Cycle 2 (Week 10), before third infusion Cycle 3 (Week 19), before first infusion Cycle 4 (Week 25), before infusion Cycle 6 (Week 49) and 30 days after discontinuation of study drug (or until patient starts new anti-cancer therapy). **All pre-dose trough samples should be drawn within 24 hours before infusion of MK-3475. (AS OF 12/11/2017 PKADA SAMPLING HAS BEEN DISCONTINUED. SPECIMENS ALREADY COLLECTED MUST STILL BE SHIPPED.)**
- r. Cover Sheet, FACT-BRM, EQ-5D-3L and FACIT-D should be completed 24 weeks (\pm 2 weeks) and 48 weeks (\pm 2 weeks) after the date of last treatment.
- s. If relapse occurs before 48 weeks after date of last treatment, Cover Sheet, FACT-BRM, EQ-5D-3L and FACIT-D should be completed at the time of relapse.
- t. History prior to each treatment initiation to include a menstrual, sexual and contraceptive use history, including date of last menstrual period (for women of childbearing potential) which will help determine the need for pregnancy testing. Similar questions regarding contraceptive use to be asked of men who are sexually active with women of childbearing potential. Height is only required at baseline.

* These are the corresponding weeks if there are no dose delays.

v Patients with history of CHF or who are deemed at risk because of underlying cardiovascular disease or exposure to cardiotoxic drugs should have an ECHO prior to treatment and an ECHO and EKG at the start of each cycle, as clinically indicated. Patients who have evidence at baseline (or subsequently) of CHF, MI, cardiomyopathy, or myositis cardiac evaluation (NYHA I/II) should have additional consult by a cardiologist, including review of EKG, CPK, troponin, ECHO cardiogram, as clinically indicated.

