9.1 Arm 1: Interferon alfa-2b (contd)

REQUIRED STUDIES	Induction Phase ^a Days 1-5 (M-F) of Weeks 1-4				Maintenance Phase ^a Days 1, 3, 5 (M, W, F) of Weeks 5-52												Post-treatment F/U prior to relapse ^c	F/U post relapse ^d		
	Cycle 1				C2			C3			C4			C5						
	Pre-study screening	Ran-domiza-tion	W 1	W 2	W 3	W 4	W 5	W 6	W 7	W 1	W 19	W 25	W 31	W 37	W 43	W 49				
X-RAYS AND SCANS	Reg Step 1	Reg Step 2																		
Whole Body PET/CT or CT neck, chest abdomen & pelvis ^k										X	X						X ^{j,k}			
Brain MRI or CT with Contrast ^k			X														X ^k			
EKG ^h																				
Image Submission ^o			X							X	X						X			
SPECIMEN SUBMISSION																				
Slides for PD-L1 Expression ^l		X																		
E-mail confirmation tissue was adequate for PD-L1 analysis ^l			X																	
Tissue ^m for banking			X														X			
Serum ^m for banking			X ⁿ							X	X						X			
Plasma & Buffy Coat ^m for RNA/DNA for banking										X	X						X			
TREATMENT																				
Interferon alfa-2b					X	X	X	X	X	X	X	X	X	X	X	X				

Click here for [footnotes](#).

NOTE: Forms are found on the protocol abstract page of the SWOG website (www.swog.org). Form submission guidelines are found in [Section 14.0](#).

NOTE: Unless indicated otherwise in the protocol, scheduled procedures and assessments (treatment administration, toxicity assessment for continuous treatment, disease assessment, specimen collection and follow-up activities) must follow the established SWOG guidelines as outlined in <https://www.swog.org/sites/default/files/docs/2017-10/Best%20Practices%20update.pdf>.

Footnotes for Study Calendar 9.1: Arm 1 (Interferon alfa-2b)

- a. The following exams and labs are done weekly during induction (Weeks 1-4 of Cycle 1), the first week of maintenance (Week 5 of Cycle 1), then every first and seventh week of each subsequent cycle until end of protocol treatment: physical (w BSA, BP & WT), PS, toxicity notation, ANC, platelets, Hgb, total bilirubin, AST and ALT, alk phos, serum creatinine or CrCl, albumin, glucose, Na, K, HCO₃ (or CO₂). Adverse Event Assessments on the study will continue for all patients until 30 days after the last study drug administration. However, patients with ongoing toxicities should be seen more often as clinically indicated.
- b. End of treatment assessment occurs at Week 53 or whenever patient comes off treatment.

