9.2 Arm 1: Ipilimumab (contd.)

		ON TREATMENT ^a																					
		Pre-Study Screening		Randomization		Induction		C		C		C		C		C		C		C			
		Reg Step 1	Reg Step 2	Cy 1	Cy 2	3	4	5	C6	7	8	9	10	11	12	13	14	15	16	17	18	19	
*				W	W	W	W	W	W	W	W	W	W	W	W	W	W	W	W	W	W	W	
	X-RAYS AND SCANS			1	4	7	10	13	25	37	49	61	73	85	97	109	121	133	145				
	Whole body PET/CT or CT neck, chest, abdomen & pelvis ^k	X				X	X	X															
	Brain MRI or CT with contrast ^k	X																					
	EKG ^h	X																					
	Image Submission ^p	X				X	X	X															
	SPECIMEN SUBMISSION																						
	Slides for PD-L1 expression ^l	X																					
	E-mail confirmation tissue was adequate for PD-L1 analysis																						
	Tissue ^m for banking	X																					
	Serum ^m for banking	X ⁿ																					
	Plasma & Buffy Coat ^m for RNA/DNA for banking																						
	TREATMENT			X	X	X	X			X	X	X	X	X	X	X	X	X	X	X	X	X	
	Ipilimumab																						

[Click here for footnotes.](#)

NOTE: Forms are found on the protocol abstract page of the SWOG website (www.swog.org). Form submission guidelines are found in [Section 14.Q](#).
 NOTE: Unless indicated otherwise in the protocol, scheduled procedures and assessments (treatment administration, toxicity assessment for continuous treatment, disease assessment, specimen collection and follow-up activities) must follow the established SWOG guidelines as outlined in <https://www.swog.org/sites/default/files/docs/2017-10/Best%20Practices%20update.pdf>.

Footnotes for Study Calendar 9.2: Arm 1 Ipilimumab

- a. The following exams and labs are performed prior to receiving first dose and at the start of every cycle until end of protocol treatment: physical (w BSA, BP & WT), PS, toxicity notation, ANC, platelets, Hgb, total bilirubin, AST and ALT, alk phos, serum creatinine or CrCl, albumin, glucose, Na, K, HCO₃ (or CO₂). Adverse Event Assessments on the study will continue for all patients until 30 days after the last study drug administration. However, patients with ongoing toxicities should be seen more often as clinically indicated.
- b. End of treatment assessment occurs at the 15th infusion or whenever patient comes off treatment (treatment stops at the end of Year 3, even if the patient has not received all 15 infusions).

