13.0 REGISTRATION GUIDELINES

13.1 Registration Timing

a. STEP 1 Registration - Screening

Patients must meet the eligibility criteria in the Step 1 Registration criteria in [Section 5.0](#). Patients must be registered within 7 business days prior to submission of specimens for PD-L1 testing. Patients must be registered within 98 days of the last surgery performed to render the patient free of disease.

b. STEP 2 Registration – Randomization

Patients who meet the eligibility criteria as stated in the Step 2 Registration criteria in [Section 5.0](#) will be registered to STEP 2 – Randomization. Patients must register within 7 working days after receiving the e-mail notification confirming that their tissue sample was adequate for PD-L1 testing.

Patients must be randomized prior to the initiation of treatment (no more than 5 working days prior to the planned start of treatment).

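### Routine adverse event assessment stops 30 days after the last dose, before antibody completers' first post-treatment visit at nominal Day 35-49, so late low-grade immune events are probably undercounted

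*Combined protocol and SAP*

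**What the plan says.** Footnotes a, c and d of all three calendars (Sections 9.1, 9.2, 9.3) set one routine window: "Adverse Event Assessments on the study will continue for all patients until 30 days after the last study drug administration".

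Footnote b places the last on-treatment assessment:
- Pembrolizumab: "End of treatment assessment occurs at the 18th infusion or whenever patient comes off treatment".
- Ipilimumab: "End of treatment assessment occurs at the 15th infusion or whenever patient comes off treatment".
- Interferon: "End of treatment assessment occurs at Week 53 or whenever patient comes off treatment".

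After treatment, footnote c gives the same visits in every calendar: "Patients should be seen at 6 weeks (-/+ 1 week) after the last dose, then 12 weeks (-/+ 1 week) after the last dose". It adds that "The first two follow-up visits may be scheduled to allow follow-up visits and scans to occur on the same date for on-going follow-up". These visits require a physical examination, blood counts and organ-function labs. The thyroid footnotes require testing at screening, Weeks 13, 25 and 37, and the first post-treatment visit, with more if clinically indicated. Footnote a's list of examinations includes toxicity notation; footnote c's list does not.

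On timing of immune events, Section 8.4a says that pembrolizumab events can appear months after the final dose. Footnote 2 to the ipilimumab adverse event list in Section 3.2c says that most appear early during treatment and a minority weeks to months after stopping.

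Section 14.4f asks for the S1404 Adverse Event Form after each cycle, and 14.4i within 7 days of stopping treatment. Section 14.4j adds a Late Effects Form for Grade 3 or higher. Section 11.7b, on the analysis of toxicity, states no collection window.

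**The concern.** The first post-treatment visit is where late thyroid, liver or renal effects would be picked up in a patient who completed an antibody, and by then the routine window has closed. A new Grade 1 or non-hospitalised Grade 2 finding at that visit has no clearly assigned routine form, so it may not enter the toxicity tables. On the control drugs the same applies to a hospitalised Grade 2 event, because the late expedited rule there (Table 16.2) covers only attributed deaths.

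Safety and tolerability is a secondary objective (Section 1.2c). Section 11.5 also makes the toxicity comparison part of the judgement of clinical benefit. What is at stake is the completeness of low-grade immune toxicity in Section 11.7b. No primary endpoint is affected.

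**Working it through.** **1. Last dose (completers, no delays).** Pembrolizumab: Cycles 1-5 hold 2+2+4+4+4 = 16 infusions, and the last 2 are half of Cycle 6. This reproduces the 18 infusions and 5.5 cycles in Section 9.3. The 18th infusion is 17 × 21 = 357 days after the first (Week 52). Ipilimumab: 4 + 11 = 15 doses, the last in Week 25 + 12×10 = 145, which is 1,008 days after the first. Interferon: last dose on Day 5 of Week 52, study day 51×7+5 = 362.

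**2. Visits against the window.** First visit: 42 ± 7 = Day 35-49 after the last dose, or 5-19 days after Day 30. Second visit: 84 ± 7 = Day 77-91, or 47-61 days after Day 30. Interferon differs: Week 53 is study days 365-371, so its end-of-treatment assessment falls 3-9 days after the last dose, inside the window.

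**3. Can alignment with scans move a visit inside the window?** Scans run from randomisation, and Section 13.1b allows at most 5 working days (taken as 0-7 calendar days) before treatment starts.
- Pembrolizumab: last infusion 357-364 days from randomisation; next body scan 60 ± 2 weeks = 406-434 days. Gap: 406−364 = 42 to 434−357 = 77 days.
- Ipilimumab: last infusion 1,008-1,015 days; scan at 3 years ± 4 weeks = 1,068-1,124 days. Gap: 53 to 116 days.
- The annual brain scan at 52 ± 4 weeks (336-392 days) can fall in Days 1-30 on pembrolizumab, but no visit is required with it.

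The one other planned contact, the Day-30 pembrolizumab PK/ADA draw (Section 15.4), was stopped on 12/11/2017.

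**4. Thyroid testing.** From Week 37 to the last dose is 52−37 = 15 weeks (pembrolizumab) or 145−37 = 108 weeks (ipilimumab). Adding 6 weeks, the first scheduled test since Week 37 comes about 21 or 114 weeks later, after the window has closed.

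**5. What else captures late events.** The Late Effects Form takes Grade 3 or higher, before relapse treatment or non-protocol therapy. After Day 30, expedited reporting takes attributed serious pembrolizumab events, including hospitalised Grade 2, and attributed deaths on the control drugs. Questionnaires at 24 and 48 weeks record symptom burden.

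**6. Size under an assumption.** The documents give no rate of late Grade 1-2 events. Let s be the share of a low-grade toxicity's first detections that come after Day 30, set at 5%, 10% or 25% (well below half, since most ipilimumab events are said to start early). Then P(seen at least once) = 1 − (1 − p(1 − s))^n, and reported rate = r(1 − s). The s = 0 column reproduces the 99% and 96% in Section 11.7b.

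| | s = 0 | 5% | 10% | 25% |
|---|---|---|---|---|
| p = 0.8%, n = 620 (pembrolizumab) | 99.3% | 99.1% | 98.9% | 97.6% |
| p = 1%, n = 310 (ipilimumab) | 95.6% | 94.8% | 93.9% | 90.3% |
| True rate 10% reported as | 10% | 9.5% | 9.0% | 7.5% |
| True rate 20% reported as | 20% | 19% | 18% | 15% |

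Section 11.7b gives precision of ±4 points for pembrolizumab and ±6 for ipilimumab. Only the 5-point shortfall (20% reported as 15%) exceeds ±4, and none exceeds ±6. The table applies s to all patients, not only completers, so it is not a completer-specific estimate.

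**The case against.** The 30-day window is explicit, the same for every regimen, and matches the base period in Tables 16.1 and 16.2. A window need not end at a visit: nothing bars a telephone assessment, or recording at Week 6 an event that began by Day 30, and patients with ongoing toxicity are to be seen more often. Patients who stop early are assessed when they come off treatment, which can be after the last dose. All of this stands and narrows the point to completers and to events first detected after Day 30.

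Two items cannot be read. The calendar grids are broken, so it is unknown whether the combined performance status and toxicity row is marked at follow-up, and the content of the Adjuvant Melanoma Follow-Up Form is not shown. The calendars also defer to external group guidelines that are not in the documents.

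A reader might infer that severe late immune events are lost. The documents do not support this, given the Late Effects Form and the expedited rules.

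A reader might also infer that collection differs between arms. Read literally, 14.4f runs to the end of a final 12-week cycle: 59 days after the last dose for interferon, 63 for pembrolizumab and 84 for ipilimumab. The largest gap, 84−59 = 25 days, is between two regimens inside Arm 1. It also treats a submission schedule as if it set the collection window. If pembrolizumab ends on the half cycle implied by 5.5 cycles, its figure is 21 days. The footnotes give one 30-day rule for all patients, so no between-arm difference in window is established.

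**Conclusion.** The point holds in a limited form. For antibody completers, the scheduled examination best placed to find late immune effects comes after routine adverse event assessment has ended, and the protocol itself expects some effects to start that late. Some undercount of Grade 1 and non-hospitalised Grade 2 events, and of hospitalised Grade 2 events on the control drugs, is likely. Its size and its net direction between arms are unknown, so it should not be read as a bias favouring either arm.

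Under the assumed 5-25% late share, most shortfalls stay within the plan's stated precision. The conclusion rests on the nominal schedule without dose delays, and on the unread follow-up row and Follow-Up Form not already collecting these events. It is a cheap improvement.

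**What to change.** - **Sections 9.1-9.3, footnotes a, c and d:** continue all-grade adverse event assessment through the existing 6- and 12-week post-treatment visits in every arm, stopping at new anti-cancer therapy if that comes first.
- **Section 14.4:** require the S1404 Adverse Event Form and Laboratory Values Form after each of these two visits, and say how 14.4f and 14.4i apply to the final cycle.
- **Section 11.7b:** use this one window for all regimens, name the data sources including the Late Effects Form, and tabulate immune events with onset after the last dose separately.

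**Cost:** no new visit, test or staff, and no change to expedited timelines. Two forms at two visits is up to four per patient: at most 4 × 1,240 = 4,960 forms for eligible patients, or 4 × 1,378 = 5,512 for all registered. Reported toxicity rates would rise slightly. Events after Week 12, or after new therapy, would stay outside the window.

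Appendix 18.8d already reports observed immune event rates, so treatment may be over. In that case the only change still possible is to state the 30-day window and its limitation in Section 11.7b.
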